**Figure 1. Study Schematic**

The treatment duration will be 12 weeks for all subjects except HCV GT1a-infected subjects with cirrhosis; these subjects will receive treatment for 24 weeks.

The duration of the study will be 156 weeks (for subjects receiving a 12-week treatment) or 168 weeks (for subjects receiving a 24-week treatment), not including a screening

period of up to 42 days, consisting of a 12-week or 24-week Treatment Period and a Post-Treatment (PT) Period of 144 weeks in total for all subjects who receive at least one dose of study drug.

Subjects who meet the eligibility criteria will be enrolled in Part 1 or Part 2 to either 12 or 24 weeks of combination therapy with or without RBV based on HCV genotype, subtype, and cirrhosis status as described in [Table 1](#).

### **Treatment Period**

**Table 1. Treatment Regimen and Duration by HCV Genotype, Subtype, and Cirrhosis Status**

Patient Population	Treatment	Duration
Genotype 1b with or without compensated cirrhosis	ombitasvir + paritaprevir + ritonavir + dasabuvir (approved adult 3D formulation)	12 weeks
Genotype 1a,* without cirrhosis	ombitasvir + paritaprevir + ritonavir + dasabuvir + ribavirin (approved adult 3D formulation plus RBV)	12 weeks
Genotype 1a,* with compensated cirrhosis	ombitasvir + paritaprevir + ritonavir + dasabuvir + ribavirin (approved adult 3D formulation plus RBV)	24 weeks
Genotype 4 with or without compensated cirrhosis	ombitasvir + paritaprevir + ritonavir + ribavirin (approved adult 2D formulation plus RBV)	12 weeks

\* Follow the genotype 1a dosing recommendations in patients with an unknown genotype 1 sub-genotype or with mixed genotype 1 infection.

All GT1- and GT4-infected adolescent subjects in Part 1 and Part 2 will receive OBV/PTV/r 25/150/100 mg once daily (QD) and GT1-infected adolescent subjects in Part 2 will receive also DSV 250 mg twice daily (BID). All adolescent subjects with HCV GT1a or GT4 infection will also receive RBV 1000 mg BID if weight is less than or equal to 75 kg or 1200 mg BID if weight is above 75 kg.

For subjects receiving mini-tablet formulation in Part 1, the doses will be dependent on the weight group (15 to 24 kg, 25 to 29 kg, 30 to 44 kg,  $\geq 45$  kg) at enrollment.

The Treatment Period will include assessment of PK, antiviral response, growth and development outcomes (assessed by height and Tanner pubertal stage), patient reported

---

outcomes (assessed by EuroQol 5 Dimensions 3 Levels Health State Instrument [EQ-5D-3L] questionnaire), HCC (assessed by liver ultrasound only in subjects with cirrhosis), acceptability questionnaires (for subjects receiving the min-tablet formulation only), and progression of liver disease (assessed by Fibrotest).

### **Post-Treatment Period**

All subjects who receive at least one dose of study drugs will be monitored for an additional 24 weeks following the last dose of study drugs in Part 1 or Part 2. All subjects who complete the PT Week 24 visit in Part 1 or Part 2 will be followed till PT Week 144 in Part 3.

The Post-Treatment (PT) Period will include assessment of antiviral response, growth and development outcomes (assessed by height and tanner pubertal stage), patient reported outcomes (assessed by EuroQol 5 Dimensions 3 Levels Health State Instrument [EQ-5D-3L] questionnaire), HCC (assessed by liver ultrasound only for subjects with cirrhosis), and progression of liver disease (assessed by Fibrotest).

The PT Period will begin the day following the last dose of study drug treatment.

### **4.3 Sample Size**

The sample size of 36 subjects in Part 1 will adequately characterize the pharmacokinetics of the AbbVie DAAs to enable dose selection in pediatric subjects.

According to the Prescribing Information of PEGASYS, the SVR24 rate in the NV17424 trial was 47% among 45 treatment-naïve pediatric subjects with HCV GT1. To show that the DAA regimen is superior to this standard of care by 20% in Parts 1 and 2, the lower bound of the 2-sided 95% confidence interval of the SVR12 rate across all subjects in the study must be greater than 67%. For the primary efficacy endpoint of the percentage of subjects with SVR12, if it is assumed that 90% of subjects would achieve SVR12 then 50 or more subjects would have > 90% power to have a lower bound of 2-sided confidence interval based on normal approximation to the binomial distribution > 67%.

#### **4.4                   Planned Analysis**

An interim analysis will occur after all subjects in Part 1 or Part 2 have completed the PT Week 12 Visit or prematurely discontinued from study. The database will be versioned after performing appropriate data cleaning. Final data through PT Week 144 will be locked in a later version of the database. SAS® (SAS Institute, Inc., Cary, NC) for the UNIX operating system will be used for all analyses. All statistical tests and all confidence intervals will be two-sided with an  $\alpha$  level of 0.05.

All analyses will be conducted by statisticians and statistical programmers at AbbVie or their designees according to the methodologies specified in this SAP.

There is no intention of changing the study design based on efficacy findings from the PT Week 12 interim analysis. The intention is to follow all subjects who receive study drug for at least 144 weeks following treatment. There will be no statistical adjustment employed due to this interim analysis.

### **5.0                   Analysis Populations**

#### **5.1                   Definition for Analysis Populations**

##### **5.1.1               Intention-to-Treat (ITT) Population**

The intention-to-treat (ITT) population will consist of all subjects who receive at least one dose of study drug in Part 1 or Part 2 of the study. All data from Part 1, Part 2, and Part 3 will be combined together, as appropriate, for statistical analyses specified in the SAP.

Demographic, baseline characteristic, exposure, concomitant medication and medical history analyses will be performed in the ITT population by age and weight group and overall among subjects on the mini-tablet formulation (ITT mini-tablet table with 6 columns), and in summary tables, by Part 1 vs Part 2 and overall for subjects on the adult formulation and overall among subjects on the mini-tablet formulation, and overall among all subjects (ITT summary table with 5 columns). Efficacy endpoints, growth and

development outcomes, and patient reported outcomes will be summarized in the ITT population. Acceptability questionnaire will be summarized overall and by age group among subject on the mini-tablet formulation in the ITT population.

In addition, sensitivity analyses of the percentage of subjects with SVR12, will be performed on the Modified Intent-to-Treat Genotype (mITT-GT) population, and Modified Intent-to-Treat Genotype and Virologic Failure (mITT-GT-VF) population, respectively, as defined below.

The mITT-GT population includes subjects who receive at least 1 dose of study drug in Part 1 or Part 2 but excludes the subjects in Part 1 who are not of HCV GT1 infection and subjects in Part 2 who are not of HCV GT1 or GT4 infection. The mITT-GT population is used to reduce the risk of bias that could occur due to enrolled population deviating from the treatment regimen as specified by the protocol.

The mITT-GT-VF population includes all subjects who receive at least 1 dose of study drug but excludes the subjects in Part 1 who are not of HCV GT1 infection and the subjects in Part 2 who are not of HCV GT1 or GT4 infection and in either part excludes subjects who did not achieve SVR12 for reasons other than on treatment virologic failure or relapse. The mITT-GT-VF population is used to reduce the risk of bias that could occur due to either discordant HCV genotype or failures unrelated to study drug.

### **5.1.2 Safety Population**

All subjects who receive at least one dose of study drug in Part 1 or Part 2 will be included in the safety population, which will be the same as the ITT population for this study.

Safety analyses will be performed on the safety population by age group and overall among subjects on the mini-tablet formulation, by Part 1 vs Part 2 and overall among subjects on the adult formulation, and overall among all subjects (Safety Summary 7 column table).

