**Safety:**

All safety analysis will be done by age and weight group separately for each formulation, for all subjects, and for all subjects on the adult formulations.

The number and percentage of subjects reporting treatment-emergent adverse events will be tabulated by MedDRA system organ class and preferred term. Tabulations will also be provided in which the number of subjects reporting an adverse event (MedDRA preferred term) is presented by grade (Grades 1 – 5) and relationship to study drugs.

Change from baseline in laboratory tests and vital sign measurements to each time point of collection will be summarized descriptively. Laboratory test and vital sign values that are potentially clinically significant, according to predefined criteria, will be identified and the number and percentage of subjects with potentially clinically significant values during treatment will be calculated.

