#### *Dose Adjustment Considerations for Part 1*

For each subject, the initial dose of DAAs will be based on the subject's body weight at Screening. No dose adjustments of DAAs or RBV will be made as a consequence of weight change during the treatment period. Dose adjustments may be implemented during the treatment period based on available data and enrollment. When preliminary pharmacokinetic and clinical data (following Week 2 intensive PK sampling or Week 8 trough sample) from approximately 6 subjects in the age group are available, these data will be used to adjust doses, if needed, for subjects who have been enrolled and for subjects who are subsequently enrolled in the respective age group. The data from age groups of  $\geq 3$  to 8 and  $\geq 9$  to 11 years old may be combined for final analyses if exposures from these 2 groups are comparable to each other.

For each of the analytes (OBV, PTV, RTV, or DSV), the geometric mean and individual values of AUC from these pediatric subjects from the Week 2 intensive PK sampling will be compared with the range of geometric means and the range of individual AUCs across Phase 1/2/3 studies in adults that had intensive pharmacokinetic data. Dose adjustments may be made for each component of the DAA regimen if the respective geometric mean AUC in pediatric subjects is outside the geometric mean range in adults and/or at least 2 of 6 pediatric subjects have individual AUCs outside of the individual range in adults. In

addition, if data are available from fewer than 6 subjects and if at least 2 of these subjects have individual AUCs outside of the individual range in adults, dose adjustment might be considered for the age group.

AUC will be the primary measure for dose adjustment.  $C_{max}$  and  $C_{trough}$  will be considered for safety and efficacy using the same rules.

Additional criteria may be considered for making dose adjustment decisions for Part 1 to ensure safe and efficacious exposures. Subjects who take at least one dose of the study drug will be followed in Part 1 of the study through Post-Treatment Week 24 to assess  $SVR_{12}$  and  $SVR_{24}$ .

### Part 2

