### **8.1.6 Safety**

All subjects who receive at least one dose of study drug will be included in the safety analyses. The safety analysis will be carried out for all subjects by formulation, age and weight group, for all subjects on the adult formulation. A listing of any SAEs recorded in Part 3 will be included.

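### SAP safety tables split mini-tablet children by age only, whereas the protocol requires age and weight group and weight band sets the dose

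*SAP*

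**What the plan says.** **Protocol.** The synopsis, under Safety, says: "All safety analysis will be done by age and weight group separately for each formulation, for all subjects". Section 8.1.6 says: "The safety analysis will be carried out for all subjects by formulation, age and weight group". Both also ask for a summary of all subjects on the adult formulation.

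**SAP safety layout.** Section 5.1.2 says: "Safety analyses will be performed on the safety population by age group and overall among subjects on the mini-tablet formulation". It then adds Part 1, Part 2 and an overall column for the adult formulation, and ends with "overall among all subjects (Safety Summary 7 column table". Section 11.1 applies this format to the whole safety analysis. Section 8.0 applies it to disposition and Section 9.0 to exposure and compliance.

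**SAP age-and-weight layout.** Section 5.1.1 defines a six-column table for mini-tablet subjects by age and weight group, and names exposure among the analyses that use it. Weight group is also kept for the SVR and ALT endpoints (10.4), subgroups (10.5), treatment failures (10.8) and the acceptability questionnaire (10.12).

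**Dosing.** Protocol 5.1 says that "the initial dose of DAAs will be based on the subject's body weight at Screening". SAP 4.2 says that for mini-tablets "the doses will be dependent on the weight group", and takes that group at enrollment.

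**The concern.** The SAP drops a grouping that the protocol promises in two places, and gives no reason. The dropped factor is the one that fixes a mini-tablet child's dose.

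The tables affected are those where dose could matter. Protocol 3.0 attributes bilirubin rises partly to paritaprevir, and Protocol 6.1.7.5 reports ALT elevations with paritaprevir-containing regimens. If events or laboratory abnormalities cluster in one weight band, the planned tables will not show it directly. A reader would have to match listed subjects to their weight or dose by hand.

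It looks like an oversight, although that is inference. Protocol Appendix F shows that weight group was added to the 8.1.6 wording in the current amendment. Elsewhere the SAP follows that amendment (62 subjects, no pellets, the 100 IU/mL breakthrough threshold).

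**Working it through.** **1. Does the stated column count leave room for weight?** The inputs are the groups in SAP 5.1.2 and the two mini-tablet age groups in SAP 4.2 (3 to 8 and 9 to 11 years).

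- Safety table: 2 age groups + 1 mini-tablet overall + 2 adult-formulation parts + 1 adult overall + 1 all subjects = 7. This reproduces the SAP's figure, with no weight column.
- The same table with three weight columns added: 2 + 3 + 1 + 2 + 1 + 1 = 10.
- Six-column mini-tablet table in SAP 5.1.1: 2 age + 3 weight + 1 overall = 6. This also reproduces the SAP's figure. It shows age and weight side by side; a crossed table would need 2 × 3 + 1 = 7.

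**2. How far do doses differ between bands?** Initial doses are from Protocol Table 11.

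| Drug | 15–29 kg | 30–44 kg | ≥ 45 kg | Middle / low | High / middle | High / low |
|---|---|---|---|---|---|---|
| Paritaprevir QD | 50 mg | 100 mg | 150 mg | 2.0 | 1.5 | 3.0 |
| Ritonavir QD | 35 mg | 70 mg | 100 mg | 2.0 | 1.43 | 2.86 |
| Ombitasvir QD | 10 mg | 15 mg | 25 mg | 1.5 | 1.67 | 2.5 |
| Dasabuvir BID | 100 mg | 150 mg | 250 mg | 1.5 | 1.67 | 2.5 |

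Per kilogram the picture changes. Paritaprevir at the band edges is 50/15 = 3.33, 50/29 = 1.72, 100/30 = 3.33, 100/44 = 2.27 and 150/45 = 3.33 mg/kg. The largest ratio among these is 3.33/1.72 = 1.93.

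**3. Can several bands fall in one age column?**

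- *Ages 9 to 11:* Protocol 5.1 asks that at least 4 of the first 6 children weigh 15 to 44 kg, so up to 6 − 4 = 2 of them may weigh 45 kg or more. The synopsis dose table for mini-tablets has a column for that weight. All three dose levels are therefore permitted in this column.
- *Ages 3 to 8:* the documents give no weight distribution. The largest paritaprevir ratio would be 1 if only one band occurs, 2.0 if the two lower bands occur, and 3.0 if all three do.

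**4. Statements that conflict on the same subject.**

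| Subject | One place | Another place |
|---|---|---|
| Exposure layout | SAP 5.1.1: six-column table, age and weight | SAP 9.0: safety format, age only |
| Mini-tablet weight bands | SAP 4.2: four (15–24, 25–29, 30–44, ≥ 45 kg) | SAP 7.1 and 10.5, Protocol Table 11: three (15–29, 30–44, ≥ 45 kg) |
| Weight that defines the band | Protocol synopsis and 5.1: Screening | SAP 4.2 and 10.5: enrollment |

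Screening may precede Day 1 by up to 42 days, so a child near a band limit could be tabulated in a band other than the one that set the dose.

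**The case against.** The best case on the other side has five parts.

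- **Listings exist.** SAP 11.2.1.1 lists treatment-emergent events with subject numbers. SAP 11.2.2 lists serious events and those leading to discontinuation or interruption. SAP 11.3.2 lists laboratory values for subjects meeting potentially clinically significant criteria, and liver tests for flagged subjects. With about 24 children, a reviewer could work from these. This stands as far as it goes: a reader might infer that toxicity by band would be invisible, and that is too strong. But those sections do not say that the listings show weight band or dose, and a listing does not replace a promised tabulation.
- **Small cells.** 24 children over three bands average 8 each, so event tables by band would be mostly zeros and ones. True, but the age columns are nearly as thin (about 12 each), and the protocol accepted this.
- **Dose decisions do not wait for these tables.** Protocol 5.1 adjusts doses by age group on accumulating data, and the SAP tables come only after Post-Treatment Week 12. This stands. The documents do not support a reading that the omission compromises dose adjustment during Part 1.
- **Weight bands aim at comparable exposure** (Protocol 5.6.5), so a gap in milligrams is not a toxicity gradient. This also stands.
- **Exposure is already covered by weight** in SAP 5.1.1. A reader might infer that the SAP omits it altogether; in fact the SAP contradicts itself.

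**Conclusion.** The mismatch is real. The protocol requires safety by age and weight group; the SAP fixes an age-only layout for mini-tablet children, and its column count rules out loose wording. Safety tables therefore cannot be read by the variable that sets the dose, except through subject listings. Disposition and compliance share the layout, although the protocol wording quoted here covers safety only.

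The size is modest. Threefold is the maximum, in absolute milligrams and for paritaprevir alone. It needs a child of 15 to 29 kg and a child of 45 kg or more in the same column. A reader might infer that every age column mixes threefold doses, or that exposure differs threefold. The documents support neither: heavier children are expressly provided for only at ages 9 to 11, and the mg/kg figures at the band edges stay within 1.72 to 3.33.

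The ratios rest on the initial three-band table in Protocol Table 11. If the four bands in SAP 4.2 are current, or doses were adjusted during Part 1, the ratios change but the missing grouping does not. No test, power figure or primary endpoint is affected. The change should be made because it restores a promised safety view at little cost.

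**What to change.** 1. In SAP 5.1.2 and 11.1, state that for mini-tablet subjects the adverse event overview, the SOC and preferred-term tables, the CTCAE grade, potentially clinically significant and hepatic laboratory tables, and the compliance table will also be produced by weight group. Use the existing age-and-weight layout from SAP 5.1.1 (2 age + 3 weight + overall).
2. Assign each child to the band given by the weight that determined the assigned dose. Reconcile Screening weight (Protocol synopsis and 5.1) with weight at enrollment (SAP 4.2 and 10.5).
3. Reconcile the four bands in SAP 4.2 with the three in SAP 7.1, SAP 10.5 and Protocol Table 11. If four apply, the layout becomes 2 + 4 + 1 = 7 columns; with three columns it would merge 15–24 with 25–29 kg. This point does not judge which set is right.
4. Reconcile SAP 5.1.1 with SAP 9.0 on the exposure layout.

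The cost is a few SAP sentences and a second run of existing table programs, with no new data. The downside is small cells, so the tables should be labelled descriptive.

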**5.2****Variables Used for Stratification of Randomization**

Approximately 62 subjects will be enrolled to receive ombitasvir, paritaprevir, ritonavir with or without dasabuvir and with or without RBV for 12 or 24 weeks depending on their HCV genotype, subtype, and cirrhotic status as shown in [Table 1](#). No other stratification of enrollment will be used for this study, although dose will depend on age group and weight group that a subject falls in.

**6.0****Analysis Conventions****6.1****Baseline and Final Value****6.1.1****Baseline**

The baseline value refers to the last non-missing measurement collected before the first dose of study drug received in Part 1 or Part 2. All assessments on Study Day 1 should be performed prior to administering the first dose of study drug, in accordance with the protocol. The baseline value is therefore determined by the last non-missing measurement collected on or before the first day of study drug administration.

If multiple measurements are recorded on the same day, the last measurement recorded prior to dosing will be used as the baseline value. If these multiple measurements occur at the same time or time is not available, then the average of these measurements (for continuous data) or the worst among these measurements (for categorical data) will be considered as the baseline value. This same baseline value will be used for Treatment and PT Periods.

Safety assessments that are collected due to a serious adverse event that occurs on the first dose day are excluded when applying this algorithm.

**6.1.2****Study Days**

Study Days (days relative to the first dose of study drug) are calculated for each time point relative to the first dose of study drug. Study Days are negative values when the time point of interest is prior to the first study drug dose day. Study Days are positive

values when the time point of interest is after the first study drug dose day. There is no Study Day 0. Study Day 1 is the day of the first dose of study drug.

### **6.1.3                    Study Drug End Days**

For all subjects who receive at least one dose of study drug, study drug end days (days relative to the last dose of study drug) are calculated relative to the last dose of study drug. The last day of study drug is defined as Study Drug End Day 0. Days before it have negative study drug end days and days after it have positive study drug end days.

### **6.1.4                    Final Treatment Value**

The final treatment value for each subject is the last measurement collected after Study Day 1 and on or before Study Drug End Day 2.

### **6.1.5                    Final Post-Treatment Value**

The final post-treatment value for each subject is the last measurement collected after Study Drug End Day 2.

## **6.2                      Analysis Windows**

For efficacy analyses of HCV RNA and resistance, the time windows specified in [Table 2](#) and [Table 3](#) describe how HCV RNA and resistance data are assigned to protocol-specified time points during the Treatment and PT Periods, respectively. All time points and corresponding time windows are defined based on the blood sample collection date.

For safety laboratory data, vital signs (except height and waist circumference and the calculation of growth rate), and health-related quality of life (QoL) PROs collected throughout the study, the time windows specified in [Table 4](#) will be used.

For height, waist circumference, the calculation of growth rate, and Tanner pubertal stage collected throughout the study, the time windows specified in [Table 5](#) will be used. The growth rate will be calculated at each visit as the change in height (millimeter) over change in age (years) from the previous visit.

For acceptability questionnaire, the time windows specified in [Table 6](#) describes how data are assigned to protocol specified time points during the treatment period.

For Fibrotest collected throughout the study, the time windows specified in [Table 7](#) will be used.

If more than one assessment is included in a time window, the assessment closest to the nominal time will be used. If there are two observations equally distant to the nominal time, the latest one will be used in analyses. The only exception to this is for the SVR windows (e.g., SVR4, SVR12, and SVR24); for these windows, the last value in the window will be used.

If multiple measurements are made on the same day for a safety laboratory parameter or a vital sign parameter, the average of the values will be used in analyses. For summaries of shifts from baseline and potentially significant values, multiple values on the same day will not be averaged; all values will be considered for these analyses.

